1.0 Objectives

1.1 Study Objectives

Describe the purpose, specific aims or objectives. State the hypotheses to be tested.

Aim 1: Pilot test the effect of Smart Ambient Bright Light (SABL) in reducing agitation in persons with dementia. We will also examine the effect of SABL on other Behavioral and Psychological Symptoms of Dementia (BPSD), affect, and sleep and side effects. We hypothesize that participants will show less agitation and other BPSD and improve affect and sleep during and after SABL compared to baseline and control periods. We will also explore the intervention effect on residents' other behavioral and psychological symptoms and affect and monitor potential side effects.

Aim 2: Evaluate the fidelity of the SABL delivery. We will evaluate the fidelity of SABL delivery. We will measure lighting intensity (lux) and circadian stimulus (CS) levels via two methods: 1) on-site light measurements, and 2) a personal light monitor. We will compare the actual lighting dosage to our target lighting dosage.

Aim 3: Evaluate the feasibility of implementing the SABL. We will use convergent mixed methods to evaluate the acceptability, feasibility, and appropriateness of the interventions from perspectives of nursing home staff and administrators.

1.2 Primary Study Endpoints

State the primary endpoints to be measured in the study.

Research typically has a primary objective or endpoint. Additional objectives and endpoints are secondary. The endpoints (or outcomes), determined for each study subject, are the quantitative measurements required by the objectives. Measuring the selected endpoints is the goal of a trial (examples: response rate and survival).

The primary outcomes of this study are 1) the effect of SABL on residents' agitation, other BPSD, affect, sleep and any side effects, 2) fidelity of SABL (e.g., lighting level on site and at individual level), and 3) feasibility of implementing SABL (e.g., acceptability, feasibility, appropriateness, time, and cost of implementing and maintaining the lighting).

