1.3 Secondary Study Endpoints

State the secondary endpoints to be measured in the study.

The secondary outcomes of this study include nursing home facility characteristics and resident characteristics.

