8.0 Number of Subjects and Statistical Plan

8.1

Number of Subjects

Indicate the maximum number of subjects to be accrued/enrolled, to include all persons who sign consent for the study. If applicable, distinguish between the number of subjects who are expected to be enrolled and screened, and the number of subjects needed to complete the research procedures (i.e., numbers of subjects excluding screen failures.)

Aims 1 and 2: Residents

Resident: The target sample size is 40 nursing home residents. We expect to screen 80 potential residents to identify and enroll 40 eligible residents.

Aim 3: Staff and Administrators

Staff: We plan to enroll 16 NH staff/administrators, including three CNAs, one activity staff, one nurse, one DON, one DOM, and one NHA.

8.2

Sample Size Determination

If applicable, provide a justification of the sample size outlined in section 8.1 to include reflections on, or calculations of, the power of the study.

Aims 1 and 2: Residents

We will recruit 40 residents with ADRD and agitation, 20 from each NH. The two NHs have at least a floor or a wing that is primarily dedicated to residents with ADRD, where we plan to

install the lighting and carry out the study. As attrition is expected to be around 10%, based on prior studies with a similar population, this will result in a final sample size of 36. This sample size was calculated based on a significance level of $\alpha=.05$, medium effect size Cohen's $d=0.53$, reported in previous studies, power=0.92.

Aim 3: Staff and Administrators

CNAs, activity staff, and nurses provide the most direct care. Priority will be given to individuals who provide care for resident participants. DONs, DOMs, and NHAs are decision makers for intervention implementation. The DOMs can provide feedback on the feasibility of installing and maintaining the lighting system and ensure the installation follows NH regulations.

Potential participants will be initially identified by NH staff and confirmed by the research team. Sample size may be increased to reach data saturation.

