8.3 Statistical or Analytic Methods

Describe the statistical methods (or non-statistical methods of analysis) that will be employed.

Aim 1

All data will initially be assessed with descriptive techniques to determine distributions and identify outliers. Baseline to post-intervention changes in participants' CMAI, NPI-NH, and ARS scores will be used as the outcomes in all subsequent analyses. To conduct the group analysis, each participant will serve as their own control, which allows minimal use of control variables. The effect of the intervention will be analyzed using multi-level modeling to adjust for clustering of participants at the facility level. We will use the daytime and nighttime average of lighting dosages (lux and CS) from the personal light monitors as the independent variable to analyze the effect of SABL on changes in CMAI, NPI, and ARS. Although not powered for a detailed analysis, we will explore the impact of participant characteristics (sex, age, race, ethnicity, ADRD stage, and daylight exposure) on the intervention effect by adding them as covariates to the regression model.

Aim 2

All data will initially be assessed using descriptive techniques to examine underlying assumptions and detect any violations. To assess the intervention fidelity, the lux and CS data measured via manual measurements will be analyzed using one sample t-tests to analyze lighting levels during the day and nighttime, compared to the target levels. The data from personal light monitors will be analyzed similarly at individual level. Although not powered for a detailed analysis, we will explore the impact of participant characteristics (e.g., sex, age, race, dementia stage, comorbidity, facility, and daylight conditions) on the lighting received based on the personal light monitor.

Aim 3

Quantitative Analysis: The data include ratings of acceptability, feasibility, appropriateness, time, and cost of installing and maintaining the intervention. All data will be analyzed using descriptive analyses. Although not powered for a detailed analysis, we will explore differences in perceptions of intervention feasibility and acceptability between sexes as well as the difference across professional roles and between facilities.

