Study Title: The Effect of Smart Ambient Bright Light for Nursing Home Residents with Alzheimer's Disease and Related Dementias (Smart Lighting Study)

PIs: [name] (Contact PI) and [name]

NCT05825404

04-24-2023

Data Analysis Plan

Aim 1: Pilot test the effect of SABL in reducing agitation in ADRD.

All data will initially be assessed with descriptive techniques to determine distributions and identify outliers. Baseline to post-intervention changes in participants' CMAI, NPI-NH, and ARS scores will be used as the outcomes in all subsequent analyses. To conduct the group analysis, each participant will serve as their own control, which allows minimal use of control variables. The effect of the intervention will be analyzed using multi-level modeling to adjust for clustering of participants at the facility level. We will use the daytime and nighttime average of lighting dosages (lux and CS) from the personal light monitors as the independent variable to analyze the effect of SABL on changes in CMAI, NPI, and ARS. Although not powered for a detailed analysis, we will explore the impact of participant characteristics (sex, age, race, ethnicity, ADRD stage, and daylight exposure) on the intervention effect by adding them as covariates to the regression model.

Aim 2: Evaluate the fidelity of the SABL delivery.

All data will initially be assessed using descriptive techniques to examine underlying assumptions and detect any violations. To assess the intervention fidelity, the lux and CS data measured via manual measurements will be analyzed using one sample t-tests to analyze lighting levels during the day and nighttime, compared to the target levels. The data from personal light monitors will be analyzed similarly at individual level. Although not powered for a detailed analysis, we will explore the impact of participant characteristics (sex, age, race, ADRD stage, co-morbidity, facility, and daylight conditions) on the lighting received based on the personal light monitor.

Aim 3: Evaluate the feasibility of implementing SABL.

The data includes ratings of acceptability, feasibility, and appropriateness. All data will be analyzed using descriptive analyses.

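### Section 1.2 ranks no outcome as the main one, and three scales may be tested against up to four light averages without a multiplicity rule, while the sample size supports one unnamed test

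*Protocol*

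**What the plan says.** - **Primary tier (Protocol 1.2).** Three groups are listed side by side: the effect of SABL on "agitation, other BPSD, affect, sleep and any side effects"; "fidelity of SABL (e.g., lighting level on site and at individual level"; and "feasibility of implementing SABL (e.g., acceptability, feasibility, appropriateness, time, and cost of implementing and maintaining the lighting". None is ranked above another.
- **Secondary tier (Protocol 1.3).** "The secondary outcomes of this study include nursing home facility characteristics and resident characteristics". These describe the sites and the sample at baseline, so no efficacy measure sits below primary.
- **Aims and design (Protocol 1.1 and 7.1).** The Aim 1 title concerns agitation. Section 1.1 is mixed: it includes other BPSD, affect and sleep in the hypothesis, then says that other symptoms and affect will be explored. Section 7.1 hypothesises about agitation only and explores other BPSD and affect.
- **Sample size (Protocol 8.2).** "This sample size was calculated based on a significance level of" .05, with d = 0.53 and power 0.92. With 10% attrition, 40 enrolled become 36. No outcome, contrast or sidedness is given.
- **Analysis (Protocol 8.3; the SAP has the same text).** "Baseline to post-intervention changes in participants' CMAI, NPI-NH, and ARS scores will be used as the outcomes in all subsequent analyses". The predictor is the "daytime and nighttime average of lighting dosages (lux and CS) from the personal light monitors as the independent variable". Neither document gives a testing order, a multiplicity rule or an alpha for these analyses.

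**The concern.** If section 1.2 is followed as written, a favourable result on agitation, other BPSD or affect, against any of the light averages, could be reported as a primary finding. The stated alpha and power describe one test, and a reader of the results could not tell which test that was. Section 1.2 also disagrees with section 7.1 on whether other BPSD and affect are primary or exploratory, so the protocol gives two answers to the question of what the trial is mainly testing.

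**Working it through.** **1. What the plan's own power figure covers.** Inputs from section 8.2: alpha .05, d = 0.53, final n = 40 × 0.9 = 36. Section 8.3 has each resident serve as their own control, so I treat d as a paired standardised difference. That is an assumption, since the protocol does not say which SD it uses.

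Paired t-test with noncentral t, df = n − 1 and noncentrality d√n. At n = 36 this is 0.53 × 6 = 3.18 on 35 df.

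| n | one-sided power | two-sided power |
|---|---|---|
| 36 | 0.930 | 0.871 |
| 40 | 0.950 | 0.905 |

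The stated 0.92 is matched closely by one one-sided paired test on 36 completers. A two-sided test comes near it only on all 40 enrolled (0.905, or 0.918 by normal approximation), which ignores attrition. A two-group comparison does not reproduce it: even with 36 per group, power is 0.60 two-sided and 0.72 one-sided. The figure therefore covers one test of one outcome, and it makes no allowance for clustering in two homes.

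**2. How many tests the plan allows.** Section 8.3 and the SAP name three outcomes. Day and night by lux and CS gives 2 × 2 = 4 light averages. The text does not say whether these enter separately or together, so the count runs from 3 (one test per scale) to 3 × 4 = 12 (the upper reading).

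**3. Chance of at least one false positive, no true effect, each test at .05.** For k independent tests it is 1 − 0.95^k.

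- One test per scale, k = 3: 1 − 0.857 = 0.143.
- CMAI alone against four light averages, k = 4: 1 − 0.815 = 0.185.
- Upper reading, k = 12: 1 − 0.540 = 0.460.

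Independence is unrealistic for the 12, because lux and CS come from the same monitor on the same resident and the scales are rated on the same person. The documents give no correlations, so I assumed a range and simulated two-sided normal test statistics (1,000,000 draws). The correlation between any two tests is the product of the scale and light correlations.

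| scale correlation | light correlation | 12 tests |
|---|---|---|
| 0.3 | 0.5 | 0.38 |
| 0.5 | 0.5 | 0.36 |
| 0.5 | 0.8 | 0.27 |
| 0.7 | 0.9 | 0.19 |

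**4. Whether a visit is fixed.** The durations in section 7.3 (1 + 4 + 2 + 4 + 2 = 13 weeks), set against visits in weeks 1, 3, 5, 7, 9, 11 and 13, put two visits inside each four-week period and one in the phase after it. The hypothesis in section 7.1 covers both during and after treatment. A SABL-minus-control contrast is therefore not yet a single test.

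**The case against.** The trial is declared a pilot, and section 8.2 claims no family-wise control. Agitation is also marked as the target: it is in the title of Aim 1 in both documents, it carries the hypothesis in section 7.1, and a CMAI threshold is an eligibility criterion. This stands to the extent that a hierarchy can be inferred. But it is not the one in section 1.2, and the protocol does state a directional hypothesis and a powered sample size.

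The count of 12 is inferred rather than stated, and 46% needs 12 separate independent tests. That stands too, which is why 12 is given as an upper reading. The problem does not depend on it, since three independent tests already give 14%.

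Analysing the light actually received is the team's declared approach (Protocol 2.3, 7.1 and 7.4.1). Choosing one light measure would settle the multiplicity as well as choosing a treatment contrast would. This stands, and the received-light analysis need not be demoted.

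Two stronger readings are tempting, and the documents support neither.

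- A reader might infer that every primary outcome is tested against four light measures, giving 5 × 4 = 20 or 7 × 4 = 28 tests. Only CMAI, NPI-NH and ARS are modelled on light. Fidelity is compared with target levels by one-sample t-tests, feasibility is descriptive in the SAP, and sleep and side effects have no stated Aim 1 analysis.
- A reader might infer that the .05 in the sample size is simply wrong. Multiplicity does not disturb the level of one test named in advance. What is missing is control across the family.

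**Conclusion.** The concern holds in this limited form. Section 1.2 leaves the primary outcomes unranked and conflicts with section 7.1. Three scales can be tested against up to four light averages with no order or multiplicity rule, and the sample size supports one test that is not identified. The family-wise error is 14% at three independent tests. At 12 tests it is 46% if independent, or about 19% to 38% if scales correlate 0.3 to 0.7 and light measures 0.5 to 0.9. Those correlations are assumptions. The error rates also take each test to be valid at .05 on its own, and the power figures ignore that there are two homes with one per sequence. The placement of baseline descriptors in section 1.3 is a labelling matter that changes no inference by itself. This should be corrected. It does not require more residents or an alpha adjustment.

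**What to change.** In section 1.2 and the SAP:

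- Name change in CMAI as the single primary efficacy outcome, tested by one pre-specified contrast or against one pre-specified light measure, at a stated visit and with stated sidedness.
- List NPI-NH, ARS and sleep as secondary, reported as estimates with 95% confidence intervals. State the sleep analysis, which is absent at present.
- Label the remaining light-measure models exploratory.
- Keep fidelity and feasibility as the separate, non-efficacy outcomes of Aims 2 and 3, and report side effects as descriptive safety.
- Move facility and resident characteristics from section 1.3 to baseline descriptors.
- Align sections 1.1 and 7.1 with this ranking.

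In section 8.2, name the outcome and the test. If it is a two-sided paired contrast, restate power at 36 completers as about 0.87 and say that this ignores clustering by home. If a light measure is chosen instead, that figure does not carry over, because the documents give no input for the power of a dose slope.

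The cost is wording, a slightly less favourable power statement if the test is two-sided, and the loss of any claim that a result on affect or other BPSD alone is a primary finding. Keeping all the tests primary under Bonferroni would cost more: two-sided power at 36 completers falls to 0.74 for three tests and 0.55 for 12.

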1.3 Secondary Study Endpoints

State the secondary endpoints to be measured in the study.

The secondary outcomes of this study include nursing home facility characteristics and resident characteristics.

2.0 Background

2.1 Scientific Background and Gaps

Describe the scientific background and gaps in current knowledge.

For clinical research studies being conducted at Penn State Health/Penn State College of Medicine, and for other non-PSH locations as applicable, describe the treatment/procedure that is considered standard of care (i.e., indicate how patients would be treated in non-investigational setting); and if applicable, indicate if the treatment, drug, or device is available to patient without taking part in the study.

Behavioral and psychological symptoms of dementia (BPSD) is significant in persons with dementia living in nursing homes. Evidence suggests that up to 90% of persons with dementia experience at least one BPSD. Agitation includes various disruptive behaviors, including verbal and physical, aggressive and non-aggressive behaviors, such as screaming, wandering, resisting, grabbing, and hitting. Among the BPSDs, agitation is the most challenging symptom. Agitation occurs in 90% of nursing home residents with dementia. Medications are commonly used as a treatment for agitation but show limited effect and have significant side effects. Non-pharmacological interventions are recommended as the first-line treatment, but most are labor-intensive and show mixed effects. Thus, identifying feasible and effective non-pharmacological interventions to reduce agitation is critical.

Researchers have tested the association between lighting and BPSD, especially agitation and depression. Evidence has shown that circadian disruption, short daylight exposure, and changes in interior daylight conditions are related to agitation. Light is the strongest external stimuli regulating the circadian rhythm, but older adults are at a higher risk for circadian disturbances and need more and brighter light to regulate their circadian rhythm because of reduced suprachiasmatic nuclei (SCN) activity and age-related vision deficiencies. In addition, persons with dementia living in nursing homes do not have sufficient daylight exposure to maintain a stable circadian rhythm. Evidence also shows that many nursing homes are too dim during the day. Therefore, ambient lighting is promising in reducing agitation in dementia, especially for older adults living in nursing home s.

Lighting interventions are not invasive with minimal adverse effects and can help maintain a stable circadian rhythm and thus reduce agitation. Traditional light interventions are light boxes that require participants to sit and keep their eyes towards the light for 1-2 hours. This can lead to compliance issues among persons with dementia and workload issues among their caregivers. Interest has arisen in using ambient lighting in nursing homes. Ambient lightings have shown positive effects on agitation in persons with dementia when targeted at 350-400 lux and circadian stimulus (CS) = 0.3-0.4. However, there are limitations among these studies that tested ambient light in persons with dementia. Window shades were closed to minimize daylight exposure and agitation was not the listed in the inclusion criteria. Daylight exposure has positive impacts on circadian rhythms, sleep quality, and depression. Yet, the daylight effects on other BPSD and affect have not been well evaluated. Additionally, intervention fidelity and feasibility are critical but has not been addressed in prior studies.

2.2 Previous Data

Describe any relevant preliminary data.

Grounded in the theoretical basis of the impact of light on circadian rhythm and aging vision, high-intensity lighting and circadian stimulation during the day and low stimulation with less short-wavelength content at night are recommended for persons with dementia. This 24-hour scheme maintains a bright-dark cycle to regulate rest/activity rhythm, reduces sleep disturbance, and consequently reduces agitation and other behavioral symptoms.

Most lighting studies design lighting interventions based on intensity and can range widely, from 350-1000 lux in the daytime for 4 to 12 hours a day. Also, the measurement method (e.g., horizontal, vertical, floor plane, work plane, or eye level) is often not explicitly specified.

Besides lux, one research group tested lighting interventions based on CS and recommended CS=0.3-0.4 during the daytime and CS≤0.1 during the nighttime.

Ambient lights showed positive effects on depressive symptoms and agitation when targeted at approximately 350-750 lux 4500-9325 K, and/or circadian stimulus (CS) of 0.375-0.4 for 10 to 12 hours a day for more than 4 weeks. For agitation specifically, it has shown positive effects when targeted at 350-400 lux and circadian stimulus (CS) = 0.3-0.4. There is also evidence on other BPSDs with mixed effects and no conclusion can be drawn. These BPSDs include pleasure, general alertness, anxious behaviors, apathy, restlessness, and disturbances of consciousness.

It is believed that our SABL is safe with minimum adverse effects based on existing research evidence. A systematic review of 32 articles concludes that bright light interventions trend toward a positive impact and do not have significant adverse effects for persons with ADRD(Mitolo et al., 2018). Two studies reported negative outcomes of lighting interventions: one study reported deteriorated agitation and depression (Barrick et al., 2010; Hickman et al., 2007) and another study reported increased anxiety (Van Hoof et al., 2009). However, their light designs were very different from this proposed study, with much higher intensity (2000-3000 lux) (Barrick et al., 2010; Hickman et al., 2007) or much higher color temperature (CCT=17000K, very bluish) (Van Hoof et al., 2009). Our proposed lighting scheme (targeted at 400 lux and CS=0.3 during the day and ≤40 lux, CS≤0.1during the night) follows the scientific consensus for persons with ADRD (Figueiro et al., 2016) and the recommendations of the American National Standards Institute and Illuminating Engineering Society (Illuminating Engineering Society of North America, 2020). Ambient light schemes similar to the proposed SABL, but without daylight incorporation, have also been evaluated in multiple studies and did not report any negative effects. (Figueiro et al., 2014; Figueiro et al., 2015; Figueiro et al., 2019; Figueiro et al., 2020) Additionally, the intensity and color of our SABL will be perceived similar to low-level daylight and does not cause any glare. Altogether, evidence suggests that our SABL is safe with minimum adverse effects.

However, there are limitations among these studies that tested ambient light in persons with dementia. Window shades were closed to minimize daylight exposure and agitation was not the listed in the inclusion criteria. Daylight exposure has positive impacts on circadian rhythms, sleep quality, and depression. Yet, the daylight effects on other BPSD and affect have not been well evaluated. Additionally, intervention fidelity and feasibility are critical but has not been addressed in prior studies. Finally, only one study reported that there were no intervention-related side effects, and most studies did not report any information on intervention side effects.

